## 7.9 Expedited Reporting

### **Reporting to the Data and Safety Monitoring Committee**

If a death occurs during the treatment phase of the study or within 30 days after the last administration of the study drug(s) and it is determined to be related either to the study drug(s) or to a study procedure, the Investigator or his/her designee must notify the DSMC Chair (or qualified alternate) within 1 business day of knowledge of the event. The contact may be by phone or e-mail.

### **Reporting to UCSF Committee on Human Research (Institutional Review Board)**

The Principal Investigator must report events meeting the UCSF IRB definition of "Unanticipated Problem" (UP) within 10 business days of his/her awareness of the event.

### **Expedited Reporting to the Food and Drug Administration**

The Sponsor-Investigator is responsible for determining whether or not the suspected adverse reaction meets the criteria for expedited reporting in accordance with Federal Regulations (21 CFR §312.32).

The Investigator must report in an IND safety report any suspected adverse reaction that is both serious and unexpected. The Sponsor-Investigator needs to ensure that the event meets all three definitions:

- Suspected adverse reaction
- Unexpected
- Serious
- If the adverse event does not meet all three of the definitions, it should not be submitted as an expedited IND safety report.

The timeline for submitting an IND safety report to FDA is no later than **15 calendar days** after the Investigator determines that the suspected adverse reaction qualifies for reporting (21 CFR 312.32(c)(1)).

Any unexpected fatal or life-threatening suspected adverse reaction will be reported to FDA no later than **7 calendar days** after the Investigator's initial receipt of the information (21 CFR 312.32(c)(2)).

Any relevant additional information that pertains to a previously submitted IND safety report will be submitted to FDA as a Follow-up IND Safety Report without delay, as soon as the information is available (21 CFR 312.32(d)(2)).

### **Reporting to Pharmaceutical Company providing Study Drug**

Any clinical adverse event or abnormal laboratory test value that is serious occurring during the course of the study from the date of signing the informed consent, irrespective of the treatment received by the patient, must be reported to the study drug sponsor within one working day of knowledge (expedited reporting). For each patient, all serious adverse events must be reported up to 30 days after the last dose of investigational product. Serious adverse events occurring more than 30 days after a patient is discontinued from the study treatment may be reported at the discretion of the investigator.

In addition to reporting to the FDA, the Sponsor-Investigator will forward completed SAE and pregnancy forms to representatives of the pharmaceutical company providing Study Drug. All forms will be completed and emailed to [[contact]](mailto:[contact])

The study drug sponsor will medically review all SAEs.

The following detailed information must be recorded for each serious adverse event in the SAE report form:

- A description of the AE in medical terms according to NCI-CTC Version 4.0, not as reported by the subject
- The severity grade as assessed by the investigator according to the definitions in NCI-CTC Version 4.0
- The date of becoming serious and the date of becoming known (if different)
- The reason for seriousness
- The outcome of the SAE at the time of the report
- Information on administration of the study drug and chemotherapy and any action taken
- Information on any treatment procedures necessary for the SAE, concomitant medications, relevant lab tests and relevant medical history

If in any one subject the same SAE occurs on several occasions, then the SAE in question must be documented and assessed anew each time.

The investigator is required to submit SAE Follow-up reports until the SAE has resolved or stabilized and all queries have been answered.

## **8 Statistical Considerations and Evaluation of Results**

### **8.1 Study Endpoints**

The primary endpoint is radiographic progression free survival (rPFS).

The secondary endpoints are to describe the following:

- PSA decline of  $\geq 50\%$  at 12 weeks post therapy initiation
- Time to PSA progression. Defined as a rise in PSA of 50% above nadir value or 25% above baseline if there is no decline.
- Relationship of abiraterone resistance status (primary vs acquired) and outcome
- Time to confirmed development of  $\geq 2$  new bone lesions that cannot be attributable to bone scan flare.
- Safety
- Exploratory endpoints are to describe the following:
  - Relationship of XPO-1 expression to PSA decline.
  - Expression profile of metastatic tumor and outcome.
  - Type of progression (e.g. Pain, bone etc)
  - Comparison of pre- and post-treatment XPO-1 expression in patients for whom pre-treatment biopsy is available through the Stand Up 2 Cancer "Dream Team" program.

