#### **2.4.2 Secondary Endpoints**

- PSA decline of  $\geq 50\%$  at 12 weeks post therapy initiation
- Time to PSA progression. Defined as a rise in PSA of 50% above nadir value or 25% above baseline if there is no decline.
- Relationship of abiraterone resistance status (primary vs acquired) and outcome
- Time to confirmed development of  $\geq 2$  new bone lesions that cannot be attributable to bone scan flare
- Reduction in pain for symptomatic patients
- Safety
- Serum selinexor levels as a function of dose and time
- Pharmacodynamic analysis of selinexor impact on XPO-1 expression, leukocyte gene expression profile, and macrophage inhibitory cytokine-1 (MIC-1) mRNA expression

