#### **Non-measurable disease (PSA)**

All patients will be evaluated for PSA decline. Patients with disease that is not measurable will be eligible for this study and will be assessed for response based on changes in PSA and serial bone scans (if appropriate). Patients who show PSA increases will not be evaluated for PSA progression prior to 12 weeks of study therapy.

**50% PSA Decline:** PSA decline of at least 50% from baseline confirmed by a second measurement at least 3 weeks later. The reference for these declines should be a PSA measured within 2 weeks prior to starting therapy.

**PSA Progression:** Prostate Cancer Working Group 2 (PCWG2) Criteria will be reported. PSA progression occurs when the PSA has increased 25% or greater above nadir and an absolute increase of 2 ng/mL or more from the nadir is documented. Where no decline is observed, PSA progression similarly occurs when a 25% increase from baseline value along with an increase in absolute value of 2 ng/mL or more. Patients will receive a minimum of 12 weeks of therapy prior to being evaluable for this endpoint. PSA progression (without evidence of progression on scans) will not be a criterion for discontinuation of study therapy.

**PSA Response Duration:** The PSA response duration commences on the date of the first 50% decline in PSA. The response duration ends when the PSA value increases by 25% above the nadir, provided that the increase in the absolute-value PSA level is at least 5 ng/mL or back to baseline, whichever is lower.

**Progressive Disease by PSA** (as defined by PSA Progression, above)

**Time to PSA Progression:** The start of the time to PSA progression is the day treatment is initiated. The end date is the time of PSA progression as defined above.

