##### Time to PSA progression (TTPP).

Time to PSA progression, is defined as the time interval between the date of treatment initiation and the date of either first documented PSA progression, or death due to any cause, whichever comes first. PSA is measured monthly until PSA progression as defined by the PSAWG2 criteria.

Duration of PSA response defined as the time between the first evaluation at which the response criteria are met and the first documentation of PSA progression or death. Early increase in PSA within 12 weeks, when followed by subsequent decline, is ignored in determining this endpoint.

Kaplan-Meier methods will be used to estimate the median time to PSA progression with a 95% confidence interval.

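### PSA progression is a 50% rise over nadir in sections 2.4.2 and 8.1 but 25% plus 2 ng/mL in 7.3, and death counts as an event in 8.4.3 but not in 7.3

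*Combined protocol and SAP*

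**What the plan says.** Four places in the combined protocol and SAP define this endpoint.

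- **Section 2.4.2 (Secondary Endpoints)**: "Defined as a rise in PSA of 50% above nadir value or 25% above baseline if there is no decline". No absolute minimum is given.
- **Section 8.1 (Study Endpoints)** repeats that rule: "Time to PSA progression. Defined as a rise in PSA of 50% above nadir value or 25% above baseline if there is no decline".
- **Section 7.3, Non-measurable disease (PSA)**: "Prostate Cancer Working Group 2 (PCWG2) Criteria will be reported", and then "PSA progression occurs when the PSA has increased 25% or greater above nadir and an absolute increase of 2 ng/mL" or more over nadir. If PSA never falls, the same 25% and 2 ng/mL apply from baseline. It adds that "Patients who show PSA increases will not be evaluated for PSA progression prior to 12 weeks of study therapy". For time to PSA progression, "The end date is the time of PSA progression as defined above".
- **Section 8.4.3, Time to PSA progression (TTPP)** runs the interval from treatment initiation to "the date of either first documented PSA progression, or death due to any cause, whichever comes first". On the criteria it says: "PSA is measured monthly until PSA progression as defined by the PSAWG2 criteria". It plans a Kaplan-Meier median with a 95% confidence interval.

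**The concern.** There are two contradictions in the current text. The first is the threshold: the endpoint lists use one rule, and section 7.3 another that differs in both the percentage and the absolute floor. The second is the event itself. Section 7.3 describes a time to PSA progression. Section 8.4.3 describes a composite of PSA progression and death.

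A programmer working from 8.1 would assign different event dates, and so possibly report a different median, from one working from 7.3 and 8.4.3. The direction depends on each patient's PSA level, so a reader of the report could not correct for it. In an open-label single-arm trial, leaving the choice until data are in hand also lets the data influence it.

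**Working it through.** The plan attaches no sample size, power or expected median to this endpoint, so there is no stated figure to reproduce. The check compares the two rules directly.

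**Thresholds after a decline** (N = nadir, ng/mL). Section 8.1: 1.5 × N. Section 7.3: the larger of 1.25 × N and N + 2. Setting 1.5N = N + 2 gives N = 4, the only point of agreement. The floor stops mattering where 1.25N = N + 2, at N = 8.

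| Nadir | 8.1 | 7.3 | Triggers first |
|---|---|---|---|
| 2 | 3 | 4 | 8.1 |
| 4 | 6 | 6 | same |
| 6 | 9 | 8 | 7.3 |
| 10 | 15 | 12.5 | 7.3 |

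**Thresholds with no decline** (B = baseline). Section 8.1: 1.25 × B. Section 7.3: the larger of 1.25 × B and B + 2. These are identical for B of 8 or more. Below 8 only the floor separates them: 7.5 against 8 at B = 6, 5 against 6 at B = 4, 2.5 against 4 at B = 2.

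**Effect on event dates.** The documents give no PSA levels or doubling times, so these are assumptions: exponential growth from the nadir (or from baseline at week 0), PSA every 4 weeks, doubling times of 8, 12, 16 and 24 weeks, and the 12-week rule of 7.3 applied to both definitions. PSA t weeks after a nadir N is N × 2^(t/DT). The event is the first sample at or above threshold, not before week 12. Entries are event weeks, 8.1 / 7.3.

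| Scenario | DT 8 | DT 12 | DT 16 | DT 24 |
|---|---|---|---|---|
| Nadir 10 at week 4 | 12/12 | 12/12 | 16/12 | 20/12 |
| Nadir 10 at week 8 | 16/12 | 16/12 | 20/16 | 24/16 |
| Nadir 10 at week 12 | 20/16 | 20/16 | 24/20 | 28/20 |
| Nadir 6 at week 8 | 16/12 | 16/16 | 20/16 | 24/20 |
| Nadir 2 at week 4 | 12/12 | 12/16 | 16/20 | 20/28 |
| Nadir 2 at week 8 | 16/16 | 16/20 | 20/24 | 24/32 |
| Nadir 2 at week 12 | 20/20 | 20/24 | 24/28 | 28/36 |
| No decline, baseline 6 | 12/12 | 12/12 | 12/12 | 12/12 |
| No decline, baseline 4 | 12/12 | 12/12 | 12/12 | 12/16 |
| No decline, baseline 2 | 12/12 | 12/12 | 12/16 | 12/24 |

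As an example, with a doubling time of 24 weeks and nadir 10 at week 8, the week-16 value is 10 × 2^(8/24) = 12.6. That passes 12.5 but not 15. The week-24 value is 10 × 2^(16/24) = 15.9, which passes 15.

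**Death.** Section 1.1 gives a median survival after progression of about 19 months. If the hazard were constant, the proportion dead by t months is 1 − 2^(−t/19):

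- Week 16 (t = 3.68): 12.6%.
- Week 24 (t = 5.52): 18.2%.

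Only deaths without earlier PSA progression change this endpoint. To illustrate the median, assume independent exponential times, a PSA-only median of 6 months and all deaths captured. The composite median is then 1/(1/6 + 1/19) = 4.6 months. With a PSA-only median of 3 or 9 months it is 2.6 or 6.1.

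**The case against.** The best defence is that the threshold conflict nearly resolves itself. Section 7.3 says the working-group criteria are the ones to be reported, and 8.4.3, which produces the estimate, points to criteria of the same kind. The bone-scan text in 7.3 uses the labels PSAWG2 and PCWG2 for the same rule. On that reading the endpoint lists are simply out of date. This is probably right, and it is why the fix adopts 7.3. But it is an inference: no text gives precedence, and 8.1 sits in the statistical section itself. The conflict over death has no such pointer.

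The size is also open to challenge. Every shift above 4 weeks, one monthly visit, comes from a doubling time of 24 weeks, and the documents describe rapidly progressive disease. Later dates apply only to patients still being sampled: treatment stops at disease progression, and the schedule has no PSA after the end-of-treatment visit. The mortality figures are crude, and entry requires ECOG 0 or 1 and a life expectancy of at least 12 weeks, so a constant hazard probably overstates early deaths. All of this stands. It limits the effect without removing it.

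Finally, 8.4.3 disregards an early PSA rise only when a decline follows, which is not the 12-week rule of 7.3. That sentence is in the paragraph on response duration, so its reach is unclear. It does not alter the two contradictions.

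**Conclusion.** Both contradictions hold. After a decline, 8.1 triggers later than 7.3 when the nadir is above 4 ng/mL and earlier when it is below. Under the stated growth and sampling assumptions the event date moves by 0 to 8 weeks in either direction, and by no more than 4 weeks at doubling times of 8 to 16 weeks. With no decline there is no difference from a baseline of 8 ng/mL upward and no shift in visit at 6. Section 8.1 is 0 to 4 weeks earlier at baseline 4 and 0 to 12 weeks earlier at baseline 2. The effect on the trial's own median cannot be calculated, because the documents give no PSA distribution. The effect of counting death is smaller than the crude mortality of about 13% by week 16 and 18% by week 24.

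The endpoint is secondary and descriptive, carries no test, and does not drive treatment, since 7.3 says PSA progression alone is not a reason to stop. The primary two-stage design is unaffected. This should be corrected before analysis, but it does not threaten the trial's main conclusion.

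**What to change.** 1. In 2.4.2 and 8.1, replace the 50%/25% wording with the 7.3 definition: at least 25% and at least 2 ng/mL above nadir, or above baseline if there is no decline, with the 12-week rule.
2. In 8.4.3, cite section 7.3 by number in place of PSAWG2.
3. Make 7.3 and 8.4.3 agree on death. Either count PSA progression only, censoring deaths at the last PSA, or count death as an event and call the endpoint PSA progression-free survival.

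The threshold change is wording only, because the monthly on-treatment PSA in section 6.1.2.4 already supports the 7.3 rule. The reported median may come out shorter or longer than under 8.1. Counting death also needs survival status. Deaths on or soon after treatment are already needed for the primary endpoint, but later ones are uncertain: section 3.5 follows patients for 30 days, and the six-monthly calls in 6.1.4 do not list survival.

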## 8.1.1 Study Design

This is a single agent, phase II open label study of selinexor in patients with mCRPC with prior therapy with standard hormone ablation agents and abiraterone. Up to 54 patients could be enrolled in the study.

## 8.2 Determination of Sample Size and Accrual Rate

### 8.2.1 Sample Size and Power Estimate

In the first stage, 18 patients will be accrued. If there are 10 or fewer patients classified as progression-free at 16 weeks in these 18 patients, the study will be stopped. Otherwise, up to 36 additional patients will be accrued for a maximum total of 54. The null hypothesis is that 55% of patients are progression-free at 16 weeks. The alternative hypothesis is 75% are progression-free at 16 weeks. The null hypothesis will be rejected if 36 or more patients classified as progression-free at 16 weeks are observed in 54 patients. There is a 60.9% chance of stopping early for futility. This design yields a type I error rate of 0.048 and power of 90.0%.

### 8.2.2 Replacement Policy

Patients removed from study for unacceptable treatment related adverse event(s) will be followed until resolution or stabilization of all treatment related adverse events to Grade 2 or lower; however, they will not be replaced.

### 8.2.3 Accrual estimates

Five patients per month are estimated to be accrued.

## 8.3 Interim Analyses and Stopping Rules

Toxicity is continuously monitored for all patients. However, a full safety assessment will also be carried out after the first ten patients have completed Cycle 1 of therapy. If 3 or more of the initial 10 patients experience grade 3 or 4 toxicity within 4 weeks of starting therapy, then accrual will be suspended. This indicates that greater than 25% of the patients have experienced unacceptable toxicity. The study may continue to proceed while the safety analysis is performed.

Additionally, in the first stage, 18 patients will be accrued. If there are 10 or fewer patients classified as progression-free at 16 weeks in these 18 patients, the study will be suspended. Further, if >33% (i.e., >6 of 18 patients) have experienced unacceptable toxicity (i.e., defined as toxicity precluding the administration of selinexor at any dose level) at the time of interim analysis, the accrual will be suspended. Otherwise, 36 additional patients will be accrued for a total of 54. There is a 60.9% chance of stopping early for futility.

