#### 1.4 Rationale for Proposed Dose

More than 200 patients with advanced cancers have received KPT-330 orally in two Phase 1 studies of KPT-330. KCP-330-001 is a dose escalation study in patients with advanced hematologic malignancies. KCP-330-002 is a dose escalation study in patients with advanced solid tumors. The DLTs were anorexia/nausea and fatigue at 40 mg/m^2 (10 times per 4-week cycle) in KCP-330-002 and the maximum tolerated dose (MTD) was 30mg/m^2. The recommended phase 2 dose (RP2D) for 10 times per cycle dosing is 30mg/m^2 in both solid and hematologic malignancies. However, pharmacodynamics analyses suggest that at doses > 6 mg/m^2, selinexor inhibits XPO1 activity for >48 hrs. Therefore a reduced intensity dosing at twice weekly (8 times per cycle) was initiated and has shown improved tolerability. Doses of 65 mg/m^2 twice weekly have cleared DLT assessment and this is the MTD in advanced solid tumors, KCP-330-002 (IND 114044). It should also be noted that a dose of 70 mg/m^2 cleared DLT in the AML arm of the ongoing Phase1 study in patients with heavily pretreated hematological malignancies (KCP-330-001, IND 11404X). The most common AEs in KCP-330-002 are GI in nature, typically fatigue (73%), nausea (70%), anorexia (57%), and vomiting (49%). Most of these AEs, which are Grade 1-2 events, are generally responsive to standard supportive care including serotonin antagonists, dopamine D2 blockers, low dose glucocorticoids, etc. Olanzapine, (or mirtazapine), megesterol acetate (Megace®), and glucocorticoids have been most useful in improving appetite in many patients treated with KPT-330. Aggressive prophylaxis with glucocorticoids, appetite stimulating agents, and anti-nausea

agents can greatly reduce or eliminate these AEs. In over >290 patients treated as of 1-April-2014, no specific organ toxicity was observed at doses  $\leq 70$  mg/m^2. Several patients have continued on single agent selinexor for >12 months.

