## 5.2 Dose Modifications and Dosing Delays

If a patient experiences an intolerable toxicity (CTCAE v4.0 Grade 3 or 4) selinexor should be held. Following resolution of the toxicity to Grade 1 or to the patient's baseline value the patient may resume treatment with study drug. In general, patients who resume therapy following toxicity should resume treatment at a lower dose level assessed to be safe. However, following recovery from toxicity that was not considered clinically important, and that could be managed if it were to recur (e.g., replacement of an electrolyte), the patient may resume therapy without dose reduction if the Investigator considers this to be in the best interest of the patient. Provisional dose levels for selinexor are listed in Table 5.2.

Management of severe or intolerable adverse reactions may require dose reduction and/or interruption of the study drug. Recommendation of dose reduction, interruption or discontinuation in the management of adverse reactions are summarized below. Clinical judgment of the treating physician should guide the management plan of each patient based on individual benefit/risk assessments.

If a patient requires a dose delay > 21 days due to a study drug-related toxicity, then the patient must be discontinued from the study unless the patient has experienced evidence of clinical benefit. If the patient has experienced evidence of clinical benefit, and in the opinion of the Investigator it is in the best interest of the patient to remain on treatment, the patient may continue on study after discussion and with approval by Karyopharm.

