### **6.1.2.3 Study Procedures, Cycle 1, Day 15**

- Serum macrophage inhibitory cytokine-1 (MIC-1) – obtained 10 minutes prior to first dose
- Leukocyte collection for XPO1 inhibition analysis - obtained 10 minutes prior to first dose, then 4 hours after first dose

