### **6.1.2.4 Study Procedures Cycle 2+, Day 1**

These procedures must be completed within 3 days of Day 1

- Physical examination
- Vital signs
- Performance status
- Evaluation of adverse events
- Concomitant medications
- Brief Pain Inventory (BPI) short form
- Imaging (CT or MRI) for tumor/lesion assessment - at completion of cycle 2, cycle 4, cycle 6, day 22-28, and then every 12 three cycles weeks thereafter
- Bone scan (Technetium) - at completion of cycle 2, cycle 4, cycle 6, day 22-28 and every 12 weeks thereafter
- Ophthalmologic exam to be performed every 3 months while on study if cataracts are identified at screening and/or as clinically indicated. This exam will include slit lamp examination and visual acuity prior to dilation, and a dilated fundoscopic evaluation and slit lamp examination. Ophthalmologic evaluations will be performed by the Department of Ophthalmology at the participating study institution.
- Laboratory evaluations
  - CBC with differential and platelet count
  - Blood chemistry assessment
  - PSA - monthly and at time of progression
  - Serum macrophage inhibitory cytokine-1 (MIC-1) – at cycles 2 and 3 – obtained 10 minutes prior to dose
  - Leukocyte collection for XPO1 inhibition analysis – at cycles 2 and 3 - obtained 10 minutes prior to dose, then 4 hours after dose

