**Table 6.1 Schedule of Study Procedures and Assessments**

Visits must occur ±7 days of planned visit unless otherwise noted.

Period/ Procedure	Screening	Cycle 1			Cycle 2 and future Cycles	End of Treatment visit	Follow- up visits
		1	3 	15			
Study Day/Visit Day	-28 to 0	1	3 	15	1	Within 30 days of last dose	By phone Every 6 months
Informed consent	X						
Baseline conditions	X						
AE assessment		X	X		X	X	X
Concomitant medications		X			X	X	X
Treatment/Drug Administration							
Selinexor		Oral, twice weekly (On Days 1 and 3 of each week 1-3 of each 4 week cycle)					
Clinical procedures							
Physical exam	X	X			X	X	
Vital signs	X	X			X	X	
Medical history	X						
Disease assessment	X				X		
Performance status	X	X			X	X	
Neurologic evaluation 	X						
Ophthalmic evaluation	X 				X 	X 	
Pulse oximetry 	X						
BPI Short Form	X	X			X	X	
Tumor biopsy(optional)	X 					X 	
Laboratory procedures							
CBC w/ Diff & platelets	X	X			X	X	
Coagulation 	X						
Blood chemistry 	X	X			X	X	
PSA	X				X 	X	
Leukocyte collection for XPO1 inhibition 		X		X	X		

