## 6.2 PK and PD Calendar

TIME POINT	Total Volume of blood (ml)	PK	PDn		
		Plasma (1 tube x 1ml)	Cytokines (1 tube x 1ml)	Leukocytes (2 PAX gene tubes x 2.5ml)	Leukocytes (1 tube x 3ml)
Cycle 1, Day 1					
Pre-dose (within 10 min before administration)	13	X	X	X	X
2 hr (~10 min) post dose	2	X			
4 hr (~20 min) post dose	7	X		X	
Cycle 1, Day 15					
Pre-dose (within 10 min before administration)	7		X	X	
4 hr (~20 min) post dose	5			X	
Cycle 2 and 3, Day 1					
Pre-dose (within 10 min before administration)	7		X	X	
4 hr (~20 min) post dose	5			X	

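### No safety laboratory test is scheduled after any of the six Cycle 1 doses until Cycle 2 Day 1; the existing Day 15 visit could carry one cheaply, as a partial remedy

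*Combined protocol and SAP*

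**What the plan says.** Section 8.3 opens with a general statement, "Toxicity is continuously monitored for all patients", and then gives a specific rule for the first ten patients: "If 3 or more of the initial 10 patients experience grade 3 or 4 toxicity within 4 weeks of starting therapy", accrual is suspended. Section 5.3 names nine toxicities to watch. Four of them are found by laboratory test: low platelets, low neutrophils, raised liver enzymes and low sodium. Table 5.3 holds or reduces doses on these values. Section 8.4.3 makes the worst grade of each laboratory abnormality a safety endpoint.

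Sections 5.3 and 4.1 refer to Section 6 for the schedule of toxicity assessment. There, blood counts and chemistry are listed at screening, Cycle 1 Day 1, Day 1 of each later cycle and end of treatment. Cycle 1 Day 3 is a telephone adverse event check. Cycle 1 Day 15 is a blood-draw visit, but Section 6.1.2.3 lists only MIC-1 and "Leukocyte collection for XPO1 inhibition analysis - obtained 10 minutes prior to first dose, then 4 hours after first dose". In Table 6.1 the Day 15 cells for adverse events, blood count and chemistry are empty, so text and table agree. For Cycle 2 Day 1, Section 6.1.2.4 says "These procedures must be completed within 3 days of Day 1".

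**The concern.** The protocol has dose rules and an early stopping rule that depend partly on laboratory values, but in Cycle 1 it schedules no value for them to use after dosing has begun. All six doses are given first, and the next scheduled test comes after the drug-free week. An abnormality that arises and recovers in that interval without symptoms may never be measured.

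Two things are at stake. A patient may take later Cycle 1 doses that Table 5.3 would have held or reduced. And the record may be incomplete: the worst-grade laboratory summary for any such event, and the 3-of-10 count for the grade 3-4 subset.

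**Working it through.** **1. Calendar.** Doses fall on Days 1 and 3 of weeks 1 to 3 (Section 5.1, Table 5.2), that is Days 1, 3, 8, 10, 15 and 17. Cycle 2 Day 1 is nominal Day 29.

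| Study day | Dose | Adverse event evaluation | Blood count and chemistry |
|---|---|---|---|
| 1 | yes | yes | yes |
| 3 | yes | telephone | no |
| 8, 10 | yes | no | no |
| 15 | yes | no (MIC-1 and leukocyte draw only) | no |
| 17 | yes | no | no |
| 29 (Cycle 2 Day 1) | yes | yes | yes |

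Scheduled laboratory gap: 29 - 1 = 28 days. Adverse event gap: 29 - 3 = 26 days. Last Cycle 1 dose to next laboratory test: 29 - 17 = 12 days.

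**2. Window.** Three days either side of Day 29 gives Day 26 to 32, or 9 to 15 days after the last dose. Day 29 is exactly 28 days after Day 1, so an on-time draw sits at the edge of the rule's four weeks. A draw on Day 30 to 32 falls after it.

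**3. Which values act where.** The thresholds in Table 5.3 and Section 8.3 differ.

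| Finding | Table 5.3 action | Counts in the 3-of-10 rule? |
|---|---|---|
| Platelets grade 2 | delay | no |
| Platelets grade 3 or higher | delay and reduce | yes |
| ALT/AST grade 2 | delay | no |
| ALT/AST grade 3-4 | delay and reduce | yes |
| Sodium grade 3 | stop, then reduce | yes |
| Bilirubin 1.5 to 3 x ULN (below grade 3) | once-weekly dosing | no |
| Neutrophils grade 3 | dose maintained | yes |

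**4. The plan's own figures.** Section 8.2.1 gives a two-stage design: 18 patients, stop at 10 or fewer; 54 in total, reject at 36 or more; 55% against 75%. With X1 ~ Bin(18, p), early stopping is P(X1 ≤ 10). Rejection is the sum over x = 11 to 18 of P(X1 = x) × P(Bin(36, p) ≥ 36 - x). This gives early stopping 0.6085 at 55%, type I error 0.0477 and power 0.9007, against 60.9%, 0.048 and 90.0% as stated. All reproduce, and none depends on the safety calendar. The plan states no operating characteristic for the 3-of-10 rule.

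**5. Illustration of lost sensitivity (assumed inputs).** Let m be the share of patients with grade 3-4 toxicity who have it only as a transient, symptom-free laboratory event, and suppose all of these are missed. The chance of suspension is P(Bin(10, p(1 - m)) ≥ 3).

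| True rate p | m = 0 | 5% | 10% | 20% |
|---|---|---|---|---|
| 20% | 32% | 29% | 26% | 21% |
| 30% | 62% | 58% | 53% | 44% |
| 40% | 83% | 80% | 76% | 67% |

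**6. Illustration of the opposite cost (assumed inputs).** With other grade 3-4 toxicity at 20%, recording laboratory-only events in a further 1, 2 or 5 percentage points of patients gives P(Bin(10, 0.21), Bin(10, 0.22) or Bin(10, 0.25) ≥ 3) = 35%, 38% or 47%, against 32%.

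**7. What a Day 15 sample adds.** The longest scheduled gap becomes 14 days for laboratory tests (1 to 15, 15 to 29) and 14 days for adverse events (15 to 29). A pre-dose sample follows four of six doses and comes 15 - 10 = 5 days after the fourth.

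**The case against.** The strongest reply is that the residue is small and cannot be measured. Section 5.3 counts spontaneous patient reports as safety data, history is taken again at Cycle 2 Day 1, and unscheduled tests are not barred, so symptomatic events are largely covered. A persistent abnormality would still be seen on Day 29. Section 1.4 reports symptomatic dose-limiting toxicity: "The DLTs were anorexia/nausea and fatigue at 40" mg/m². Table 5.3 calls neutropenia and hepatic toxicity rare and thrombocytopenia uncommon; of the laboratory toxicities at issue, only hyponatremia is called common. The starting dose is low: 60 mg is 60/2.3 = 26 to 60/1.5 = 40 mg/m² over the body surface areas in Section 1.4, against a solid-tumor MTD of 65 mg/m². The documents give no laboratory-only grade 3-4 rate, nadir time or recovery time. The events that a Day 15 test would add to the count are also the ones that could trigger suspension for values Section 5.2 treats as manageable.

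All of this stands, and it limits the point. It does not supply a measurement. Continuous monitoring and committee review can act only on results that exist, and Table 5.3 retains its laboratory rules at this dose.

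Three stronger readings are tempting, but the documents do not support them:

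- A reader might infer from the Table 6.1 header, "Visits must occur ±7 days of planned visit unless otherwise noted", that the Cycle 2 Day 1 draw can fall anywhere from Day 22 to 36. The header yields to specific rules, and Section 6.1.2.4 sets 3 days for this visit, in line with Section 6.1.
- A reader might infer that every value missing a Table 5.3 hold is also lost to the 3-of-10 count. Grade 2 platelets or ALT/AST would never enter a count restricted to grade 3-4.
- A reader might take the illustrated probabilities as evidence that the rule is materially blunted. They show only what follows if the assumed shares were true.

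**Conclusion.** The calendar gap is certain: after Cycle 1 Day 1 no blood count or chemistry is scheduled until Cycle 2 Day 1, and no adverse event evaluation after the Day 3 call. The consequence is possible rather than shown, and it is confined to transient laboratory toxicity without symptoms. Such toxicity may escape a Cycle 1 dose hold or reduction and the worst-grade summary; only its grade 3-4 part may escape the early safety count. The size cannot be derived from the documents. On assumed missed shares of 5% to 20%, and with every such event missed, the chance of suspension falls by about 3 to 12 points at a true 20% rate (32.2% to 29.2% or 20.6%) and by about 3 to 16 points at 40% (83.3% to 79.8% or 66.9%). With a share of zero it does not change. Efficacy inference is untouched. This is a cheap improvement to patient safety and laboratory ascertainment, not a flaw in the design.

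**What to change.** In Section 6.1.2.3 and Table 6.1, add a pre-dose blood count with differential and platelets, blood chemistry and adverse event evaluation to the Cycle 1 Day 15 visit, with results reviewed before the Day 17 dose. In Section 8.3, state that the four-week assessment includes the pre-dose Cycle 2 Day 1 results when they are drawn up to 3 days late within the window.

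Leave the 3-of-10 threshold as it is. If it triggers on brief laboratory values, the safety review can use the distinction Section 5.2 already draws for "toxicity that was not considered clinically important, and that could be managed if it were to recur (e.g., replacement of an electrolyte").

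The cost is two routine tubes at an existing draw, one adverse event review at a visit already attended, and a calendar amendment. There is also a modestly higher chance of suspension for manageable values. The remedy is partial: the effects of doses five and six still wait for Cycle 2 Day 1, later cycles are unchanged, and without a nadir time the share of events caught is unknown. The worst-grade laboratory summary in Section 8.4.3 should state that limit.
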